Aside from physical limitations to their exercise capacity, Fontan patient self-confidence toward physical activity is low, as is exercise participation. Studies indicate that amongst youth with CHD, low self-confidence may be a more important predictor of participation than the severity of the disease. Parental overprotection is a common finding in children with CHD with a lasting impact on patient self-confidence and anxieties toward physical activity well into adulthood. Alteration of patient and parental perception and anxieties toward participation in physical activity may improve compliance to exercise training and encourage more positive patient perceptions toward healthy lifestyle habits, including frequent physical activity participation.

Recent technological advances in remote health assessment capabilities and telehealth systems have allowed the development of medically supervised home graduated physical training for adult cardiac patient rehabilitation. The application of such technologies to pediatric congenital heart patients has not been tested. In collaboration with [name] at the Advanced Man Machine Interface Laboratory at the University of Alberta, a custom pediatric remote bike ergometer (MedBike) was developed. This technology provides the medical supervisor with a live-feed of patient video/audio, electrocardiograph (ECG), blood pressure (BP) and blood oximetry signals while enabling remote determination of patient work load through the bike ergometer. The long-term goal is to use this technology to improve patient exercise capacity and to positively influence patient and parental perceptions of the patient's physical ability.

Study Design: Prospective Cohort Study

Study Procedures:

[name] is a member of potential participants clinical care team. He has been added to the study team. Whenever he is available, he will perform early contact by telephone just as the clinic nurse would as described in this section. However, since he is a member of both the study team and the clinical care team there is no need for an early contact letter or permission to contact letter. This process is in adherence with section 55 (section 34) of the Health Information Act. This role will be documented on the delegation log.

CONFIDENTIAL

This material is the property of individual. No part of it may be transmitted, reproduced, published, or used by other persons without written authorization.

A clinic nurse will be put on the delegation log to cover [name] during any absence. For that reason the early contact letter and permission to contact letter will be maintained on this ethics approval. Whenever the clinic nurse covers for [name] early contact role, the early contact letter and permission to contact letter will be used to adhere with section 55 (section 34) of the Health Information Act. This role will be documented on the delegation log. Potential participants will be identified by clinic nurses/physician who will be made aware of the inclusion criteria. Clinic nurses will ask potential participants if they would be willing to be approached by a study investigator. If so, a clinic nurse will contact a member of the study team. Recruitment will be achieved by approaching eligible patients in the clinic by a member of the study team that is not the most responsible physician (research coordinator) to prevent undue pressure.

Given that 10 healthy adult participants will be recruited from the study team for stage 1, we will take additional steps to prevent undue pressure. The study team will be made aware eligibility. Interested persons have been asked to contact the study coordinator. The study coordinator will complete the consenting process. The study PI/team will be available for further discussion. It will be clearly stated that participation is completely voluntary and that the participant may withdraw consent at any point without it impacting their role/credit in this study, their employment or future medical care.

Study will be performed in two stages.

Stage 1 (pre study): To calibrate Medbike with reference standard cardiopulmonary exercise test (CPET), and to determine patient tolerance to maintenance of exercise intensity to varying workload in children with Fontan for planning of optimal exercise regimen.

Stage 1A: The program has two retrospective calibration samples already that will be used. Consent will not be obtained given that the data is anonymized and medical records/other identifying information will not be obtained. We will also recruit 10 healthy adult participants prospectively to calibrate the MedBike. VO₂ and CPET will be set at a constant workload between 25W and 125W. Exercise will be repeated after 2 hours of rest on the Medbike with the same setting and VO₂ measures. This visit will take 3 hours to complete.

Stage 1B: We will recruit 10 patients with Fontan physiology to undergo a baseline standard CPET. Consistent with standard guidelines (ATS/ACCP statement on cardiopulmonary exercise testing, Am J Respir Crit Care med 2003; 167:211-277), exercise workload will be increased progressively such that peak oxygen consumption is achieved in 8-12 minutes. Oxygen consumption, CO₂ production, ventilation, arterial saturation (SpO₂) and blood pressure will be monitored throughout each exercise test.

Stage 1B will be completed in two visits.

- Visit 1: Participants will perform a standard CPET and VO₂ will be measured. This visit will take 1 hour to complete. From the results of this baseline CPET, a high-intensity interval training (HIIT) program will be designed for the subjects (described below).
- Visit 2: Participants will perform the designed HIIT program using the MedBike. This will consist of a 5-minute warm up at 30% of the subject's peak power output (based on results of the baseline CPET study). There will then be 7 bouts of high-intensity interval bursts. Each burst will consist of 2-minutes at 70-90% of peak power output and a 1-minute rest at 40-50% of peak power output. The subjects will then end with a 5-minute cool down at 30% peak power output. An exercise physiologist will be present and will make changes to the interval bursts based on the subject's perceived difficulty and workload. The program is 30-minutes in total. We anticipate

CONFIDENTIAL

This material is the property of individual. No part of it may be transmitted, reproduced, published, or used by other persons without written authorization.

that Visit 2 will take approximately 1-hour to complete with set-up, orientation, and sizing of the MedBike to the subject. In the room with the subject will be an exercise physiologist/technician capable of troubleshooting issues with the MedBike and associated devices for data collection. There will also always be a supervising physician with training in Pediatric Advanced Life Support (PALS), who will continuously monitor the subject's vital signs and the subject's overall clinical status. A 5-10 minute questionnaire will be administered. The purpose of this short questionnaire is to learn a bit more about the participants experience using our video-game tele-medicine exercise bike, the MedBike.

Stage 1B will provide insights as to the feasibility and logistics regarding HIIT programs in the pediatric Fontan patients. This will provide critical information for the investigators as they transition to Stage 2.

Stage 2 (HIIT exercise program): We will evaluate the safety and efficacy of an 8-week, 3 times per week supervised HIIT exercise program in patients with SV physiology.

We aim to recruit 15 subjects with Fontan physiology for Stage 2. Fontan subjects who participated in Stage 1B will invited to continue to Stage 2. If they choose to continue with the HIIT exercise program, Visit 2 of Stage 1B will serve as their first session. Two MedBike exercise ergometers (one pediatric size and one adult size bike) will be housed in the University of Alberta Hospital Rehabilitation Unit with tele-health links to a remote workstation in a separate room. The patients will exercise in a room adjacent to the supervisor workstation with no direct visual or audio contact except for the video/audio feed. This is to help simulate the real-world applicability of having the MedBike at a remote location (such as the subject's home). The HIIT program described above will be applied. The exercise physiologist will again have the ability to modify the program based on the perceived difficulty or ease of it, noting changes that were made. Again, a medical personnel with training in Pediatric Advanced Life Support certification will be present supervising the sessions.

All eligible patients will undergo full cardio pulmonary exercise testing (CPET) and anthropometry assessment of lean muscle mass prior to exercise training and at the end of the training period. For subjects who participated in Stage 1 of the study, their Stage 1 CPET will serve as their initial study. We will document any adverse effects from the 240 training sessions during the study.

Exercise sessions will be based on standardized guidelines for aerobic exercise (ACSM's guidelines for exercise testing and prescription 2013). Heart rate, blood pressure, oxygen saturation and rating of perceived exertion will be monitored during each session.

Any adverse events such as profound desaturation (oxygen saturations fall of $> 10\%$ points for greater than 1 min, chest pain and ECG changes consistent with ischemia (ST depression or elevation in 2 consecutive leads), reducing blood pressure during exercise $> 20\text{mmHg}$, development of tachyarrhythmia (atrial or ventricular) and any bike injury, will result in immediate stoppage of exercise regimen and evaluation by the onsite medical personal, if necessary pediatric cardiology consultation.

The impact of the exercise program on patient and parental perceptions of the patient's physical capacity will be evaluated using qualitative methods, as well as health related quality of life questionnaires. Patient and parents will be interviewed prior to, and at the end of, the exercise training as to their perceptions of the influence of physical activity in the presence of complex CHD.

Primary outcome: Exercise capacity assessed as the change in max VO_2 pre- vs. post- completion of the HIIT exercise program. Hypothesis- we will observe an increased in VO_2 max of 15%.

CONFIDENTIAL

This material is the property of individual. No part of it may be transmitted, reproduced, published, or used by other persons without written authorization.

Secondary outcomes: a) Patient and parental perception of a CHD patient's safety and limitations while performing physical activity through a successful physical rehabilitation program; b) adverse events (safety profile of exercise program).

Inclusion Criteria:

Stage 1A – Retrospective calibration records, prospectively recruited healthy adults 18+

Stage 1B: SV patients with Fontan circulation age 10 - 18 years.

Stage 2 - SV patients with Fontan circulation age 10 - 18

Exclusion Criteria: Patients with cardiac arrhythmias, persistent low resting oxygen saturation of $< 85\%$, severe ventricular dysfunction on the most recent clinical echocardiogram, patients with reports of chest pain on exertion, and those in whom their cardiologist has restricted their exercise for any reason.

Statistical Plan

Sample Size

Stage 1A:

Two retrospective samples will be included. Ten healthy adults will be recruited prospectively.

Stage 1B:

10 patients with Fontan physiology.

Stage 2:

To detect a clinically relevant change of 15% in max VO_2 with power of 0.8, alpha of 0.05 and effect size of 1.08 with the an anticipated mean peak VO_2 28.2 ml/kg/min \pm 6.1, the calculated sample size is 9. We will recruit 15 Fontan patients in anticipation of up to 30% failure to complete study exercise regimen.

Statistical Methods:

All data will be reported as median with ranges. Comparison between pre and post exercise training data will be tested using paired Wilcoxon signed rank sum. Significance is present when $p < 0.05$.

The Research Team:

This research will be lead by [name], who is a proven investigator with 25 peer- reviewed publications in the last 5 years. The co-investigators include [name], a heart failure specialist and [name], the team lead of the Division's Single Ventricle Outcomes Team that is supported by a WCHRI- funded fulltime research coordinator. This team is also supported by the Department of Pediatrics and AHS, with 3 funded Clinical Research Fellows attached to the Division. Our collaborators [name], [name] and [name] are recognized experts in their respective fields of computing science, exercise physiology and qualitative research of family outcomes related to SV, all with extensive success in their research endeavor.

Anticipated Outcomes and Impact:

CONFIDENTIAL

This material is the property of individual. No part of it may be transmitted, reproduced, published, or used by other persons without written authorization.

We anticipate improved patient CPET performance and a potential increase in measured total lean muscle mass after completing the exercise regimen. We do not anticipate any significant adverse effect from participation in the training sessions thus confirming its safety profile. As we have already performed prototype testing of the custom remote ergometer bike during design and assembly, we do not anticipate any major equipment performance issue or failure. The qualitative research findings will help explain our quantitative findings as we will elicit detailed descriptions of experiences, attitudes, and emotions related to physical activity in children and adolescents with life-limiting/complex CHD. We expect improved health-related quality of life scores in both patient and parental report post exercise training. The impact of a successful exercise training program in pediatrics has immediate benefits in promoting physical activities in children with SV which is currently reduced and likely to continue to decline with increasing age. Exercise training promotes self-confidence and perceived improvement in quality of life. It has the potential to promote a lifetime habit of regular physical activities that is likely to positively impact on a child's long-term cardiovascular and mental health.

Future direction and Knowledge Translation:

We will disseminate our findings through national and international presentations and publications in peer reviewed scientific journals. We will use our findings to support and guide the formation of a Pediatric Cardiac Exercise Rehabilitation Program in Alberta through establishing a guiding committee to engage stakeholders in the Western Canadian Children's Heart Network, nurses, cardiologists, general pediatricians, and organizations such as the Canadian Pediatric Cardiology Association, the Canadian Pediatric Society, and the Canadian Nurses Association, health care administrators and program and policy development personnel at the local and provincial levels. At a local level, we will use the results of the study to lobby charitable foundations, Alberta Health Services, other local funding agencies and government to support the establishment of an Edmonton Pediatric Cardiac Exercise Rehabilitation Program for immediate implementation. We will link with The Children's Heart Society to disseminate our results through their social media outlets and newsletter. In addition to the immediate clinical impact for patients with SV, the findings from the study will spawn subsequent research initiatives for promotion and improvement of physical fitness in other pediatric congenital heart lesions and non-cardiac pediatric conditions with an increased life-time burden of cardiovascular risk such as patients with diabetes, obesity and other chronic disease.

CONFIDENTIAL

This material is the property of individual. No part of it may be transmitted, reproduced, published, or used by other persons without written authorization.

References:

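### In the prospective part of Stage 1A every adult rides the reference ergometer first and the MedBike second, so a second-bout effect cannot be separated from a device difference

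*Combined protocol and SAP*

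**What the plan says.** The relevant text is Stage 1A under Study Procedures in the combined protocol and SAP. The stated purpose of Stage 1, as far as the device is concerned, is to calibrate the MedBike against the reference-standard cardiopulmonary exercise test (CPET).

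- Existing data: "The program has two retrospective calibration samples already that will be used". Their size and test order are not described.
- New data: "We will also recruit 10 healthy adult participants prospectively to calibrate the MedBike".
- First bout: "VO₂ and CPET will be set at a constant workload between 25W and 125W".
- Second bout: "Exercise will be repeated after 2 hours of rest on the Medbike with the same setting", with VO2 measured again.
- Timing: both bouts fall in one visit. "This visit will take 3 hours to complete".

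The Sample Size section gives the Stage 1A numbers without a rationale or precision target. The Statistical Methods section covers only the comparison before and after training. It gives no analysis for the calibration, no agreement limit and no rule for using the result.

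**The concern.** In the ten prospective adults, device and order are completely confounded. Residual fatigue, greater ease with the procedure or time of day could change VO2 in the second bout, and any such change would appear as a property of the MedBike. Because all ten adults follow the same sequence, no later analysis of their data can separate the two, and recruiting more adults in that sequence would only estimate the mixture more precisely.

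What is at stake is the calibration itself and, by inference, the reading of training intensity. Stages 1B and 2 express interval workloads as percentages of peak power from the baseline CPET, while the training is done on the MedBike. Those percentages are easy to interpret only if watts on the two devices correspond, and Stage 1A is the prospective check of that correspondence.

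**Working it through.** **The plan's own figure.** There is none for Stage 1A. The only calculated sample size is the 9 for Stage 2. A two-sided paired t-test at effect size 1.08 reproduces it (power 0.809 at n = 9), but this point does not depend on it.

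**Inputs from the documents.** n = 10 adults; reference bout, 2 hours of rest, MedBike bout; one sequence only.

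**Assumptions.** One paired difference per adult. Second-bout effect p of 1% to 5% of VO2. SD of the within-adult differences of 3%, 5% or 8%. The documents give none of these.

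**Step 1, bias.** Let d be the true device difference (MedBike minus reference).

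- Fixed order: every adult's difference has expectation d + p, so the mean estimates d + p. All of p enters.
- Balanced order: the reference-first group has mean d + p and the MedBike-first group d − p. The average of the two is [(d + p) + (d − p)] / 2 = d. None of p enters.
- Limit of the cancellation: if the carryover into the second bout differs by device, say a when the reference comes first and b when the MedBike comes first, the balanced estimate is d + (a − b)/2. It is unbiased only if a = b.

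**Step 2, precision.** With SD s of the differences, the fixed-order mean has variance s²/10. The balanced estimate has variance (s²/5 + s²/5)/4 = s²/10, which is the same. Only the degrees of freedom change, from 9 to 8:

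| Design | t (0.975) | 95% half-width |
|---|---|---|
| Fixed order | 2.262 | 2.262/√10 = 0.715 × s |
| Balanced 5/5 | 2.306 | 2.306/√10 = 0.729 × s |

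The ratio is 2.306/2.262 = 1.019, so the interval is about 2% wider.

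**Step 3, what the bias could do.** I simulated n = 10 with no true device difference and 40,000 runs per case. The table shows how often a two-sided 5% t-test would declare a device difference. The plan specifies no such test; the rates are only a yardstick.

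| Assumed second-bout effect | SD of differences | Fixed order | Balanced order |
|---|---|---|---|
| 1% | 5% | 9% | about 5% |
| 3% | 3% | 80% | about 5% |
| 3% | 5% | 39% | about 5% |
| 3% | 8% | 19% | about 5% |
| 5% | 5% | 80% | about 5% |

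The range is wide because it depends on two quantities the documents do not give.

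**The case against.** The case for leaving the plan alone has several parts, and much of it stands.

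- Two hours of rest separate two constant-load bouts, so fatigue may be small. That is fair, but the plan offers no evidence that the second-bout effect is zero, and rest does not remove familiarity or time of day.
- The interval band of 70–90% of peak is already 10/80 = ±12.5% around its midpoint, wider than the assumed 1–5%. The exercise physiologist can change the intervals, and heart rate, blood pressure, saturation and perceived exertion are monitored in every Stage 2 session. This limits the practical consequence. It does not make the calibration estimate correct.
- The primary outcome is the change in max VO2, measured by CPET before and after training, and device agreement is not a listed outcome. This stands: a Stage 1A order effect does not bias that measurement.

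A reader might also infer three stronger points that the documents do not support.

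- That the Stage 1A result sets the workload delivered to each patient. The prescription comes from each patient's own CPET peak power, and nothing says that the bike is rescaled from Stage 1A. Turning a percentage of VO2 into watts would also require VO2 to be proportional to workload.
- That all calibration data share the fixed order. This is shown only for the ten prospective adults. If the retrospective samples were pooled with them, the share of p that enters the combined estimate would depend on weights and an order that are not given.
- That the paediatric-size bike used in Stage 2 goes unchecked. Stage 1A does not say which size the adults ride, the background describes the MedBike as a custom paediatric ergometer, and the section on anticipated outcomes reports earlier prototype testing.

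**Conclusion.** The concern holds as a minor design point, limited to the ten prospective adults of Stage 1A. The fixed sequence makes a second-bout effect indistinguishable from a device difference, and all of that effect enters the prospective estimate. Its size and direction are unknown; the 1% to 5% of VO2 used here is an assumption. That a balanced order would cancel it follows from the design, given no device-specific carryover. The consequence reaches the calibration result and the interpretation of training intensity on the MedBike, and stops short of the primary endpoint measurement. The change is worth making because it is nearly free before testing and cannot be made up by analysis afterwards.

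**What to change.** In Stage 1A, state that the order is randomised: five adults take the reference test first and five the MedBike first, with the same 2-hour rest and the same workload setting on both devices. In Statistical Methods, state that the device difference is the average of the two order-group means of MedBike minus reference, with a 95% interval on 8 degrees of freedom. Add a sentence on how the calibration result will be used, and give the test order in the two retrospective samples or say that it is unknown.

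If any adults have already been tested in the fixed order, describe their result as device difference plus second-bout effect.

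The cost is a few sentences and an interval about 2% wider. The adults, the single visit and the measurements stay the same.

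### The hypothesis is a 15% rise in max VO2, but the plan reports the primary effect without precision and does not say how it will be read against 15%

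*Combined protocol and SAP*

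**What the plan says.** All references are to the combined protocol and SAP.

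- **Primary outcome.** The endpoint is "Exercise capacity assessed as the change in max VO_2 pre- vs. post- completion of the HIIT exercise program". The hypothesis attached to it is "we will observe an increased in VO_2 max of 15" per cent.
- **Sample Size, Stage 2.** The calculation uses the same figure: "To detect a clinically relevant change of 15% in max VO_2", "with power of 0.8, alpha of 0.05 and effect size of 1.08", with an "anticipated mean peak VO_2 28.2 ml/kg/min" and a spread of 6.1. It arrives at 9 patients; 15 are to be recruited to allow for up to 30% not completing.
- **Statistical Methods.** There are three statements. First, "All data will be reported as median with ranges". Second, "Comparison between pre and post exercise training data will be tested using paired Wilcoxon signed rank sum". Third, significance is taken at p < 0.05.

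The plan mentions no confidence interval. It does not define a percent-change estimate or say how the result will be compared with 15%. It also does not say whether the reported medians are of individual changes or of the pre and post values taken separately.

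**The concern.** The hypothesis concerns the size of a relative effect, whereas the planned test addresses only whether there is any change. Powering for 15% and testing against zero is ordinary, provided the report then gives the size of the effect and how well it is known. Here the only planned summary is the median and range. A range shows the two most extreme patients. It tends to widen as patients are added, whereas a confidence interval narrows, so it cannot stand in for one.

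The scale is also open. The hypothesis is in per cent, but the test is not tied to percent change or to absolute change. If the medians are of pre and post values separately, they do not in general give the median within-patient change.

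The section on future direction and knowledge translation says the findings will support and guide a rehabilitation programme and be used to seek funding for one. Readers making those decisions need to know which effects the data are compatible with, and anyone planning a later study needs the SD of the paired change. The planned report supplies neither.

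**Working it through.** **Inputs.** From Sample Size, Stage 2: baseline mean 28.2 ml/kg/min, SD 6.1 (read here as between-patient), target change 15%, effect size 1.08, power 0.80, alpha 0.05 (sidedness not stated; two-sided assumed), n = 9, recruitment 15, loss up to 30%. From Statistical Methods: paired signed-rank test. The SD of the paired change is not given.

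**1. Reproduce the plan's figure.** A paired t-test against zero change with effect size 1.08 and two-sided alpha 0.05 has power 0.746 at n = 8 and 0.809 at n = 9. The stated n = 9 therefore reproduces, and it does so with 15% as the alternative used for power and zero as the null.

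**2. SD of change.** The target in absolute units is 0.15 × 28.2 = 4.23 ml/kg/min. Two values bracket the working:

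- Implied by the effect size: 4.23 / 1.08 = 3.92. Using SD of change = 6.1 × √(2(1 − r)), this needs a pre-post correlation r of about 0.79.
- Equal to the only SD printed: 6.1, which corresponds to r = 0.5.

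**3. Half-width of a 95% interval.** Half-width = t(0.975, n − 1) × SD / √n, then divided by 28.2 to give percentage points of baseline. This is a t approximation for the mean; an interval from the signed-rank test will differ somewhat. The sizes are n = 9 (calculated), n = 10 (15 × 0.7 = 10.5, rounded down) and n = 15 (no loss).

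| n | t | SD 3.92: ml/kg/min | points | SD 6.1: ml/kg/min | points |
|---|---|---|---|---|---|
| 9 | 2.306 | 3.01 | 10.7 | 4.69 | 16.6 |
| 10 | 2.262 | 2.80 | 9.9 | 4.36 | 15.5 |
| 15 | 2.145 | 2.17 | 7.7 | 3.38 | 12.0 |

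The same numbers are the smallest observed mean rise that reaches p < 0.05 under the t approximation.

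**4. What an observed rise of exactly 15% would look like.**

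| n | SD 3.92 | SD 6.1 |
|---|---|---|
| 9 | 4.3% to 25.7% | −1.6% to 31.6% |
| 10 | 5.1% to 24.9% | −0.5% to 30.5% |
| 15 | 7.3% to 22.7% | 3.0% to 27.0% |

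**5. The planned test itself.** Exact signed-rank p-values were simulated for normally distributed changes with SD 3.92 and a true rise of 10%. The test is significant in about 42%, 52% and 71% of trials at n = 9, 10 and 15. Of those significant trials, about 65%, 70% and 82% have a median change below 15% of the baseline mean.

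**6. Which median.** Pre and post values were simulated for 9 patients, with a true rise of 15%, SD 6.1 at each time and r = 0.79. The percent change between the two separate medians was compared with the median of the individual percent changes. The central 90% of the differences runs from about −12 to +13 points, nearly as large as the 15% target.

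**The case against.** The strongest defence is that this is standard practice. A study is powered for a relevant difference and tested against no difference, and n = 9 reproduces on that basis. The primary outcome is the change itself and the hypothesis is worded as what will be observed, so a median change or percent change can be reported under the plan and compared with 15%. All of this stands.

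A reader might go further and infer that the plan cannot say whether 15% was reached, or that it would declare success on a smaller effect. The documents do not support either reading. A descriptive comparison remains open. The text defines when significance is present but sets no success criterion, and nowhere says that p < 0.05 would establish a 15% rise. Nor does it commit to separate pre and post medians; it is silent on the point.

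A reader might also infer that a rise of about 10% is bound to be significant. That depends on the SD of 3.92, which is back-calculated. With 6.1, an observed mean rise would have to exceed 15% to be significant at n = 9 or 10.

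Finally, it can be objected that an interval will rarely settle the question. That is fair: the half-widths are wide on either SD, and demonstrating a rise above 15% with 80% power, even with an SD of 3.92, would need a true rise of about 29.8% at n = 9 or 25.8% at n = 15. This argues against testing against 15% and for showing the uncertainty openly.

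None of these arguments supplies a measure of precision, which is the part of the concern that survives.

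**Conclusion.** The concern holds in a limited form. As written, the primary effect would be reported with no measure of precision, on a scale not fixed to within-patient change, and with nothing to show which effects around 15% the data allow. A significant result would support some change and no more.

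The choice of null and the planned test are not at fault. The absence of an interval follows directly from the Statistical Methods text and needs no assumption. The size does: across the two SDs of change considered, the 95% half-width runs from 7.7 points (SD 3.92, n = 15) to 16.6 points (SD 6.1, n = 9). Both SDs are assumptions, and the figures use a t approximation in place of the signed-rank interval. On either SD, an observed rise near 15% would leave the hypothesis unresolved, and a median with a range would not show this.

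**What to change.** In Statistical Methods:

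1. Name the within-patient percent change in max VO2 as the primary estimate.
2. Report the Hodges-Lehmann estimate with its 95% confidence interval, and run the signed-rank test on the same scale so that test and interval agree. Using log(post/pre) and back-transforming to per cent is one option; individual percent change is another.
3. State that p < 0.05 shows only some change, that the interval shows which effects, including 15%, are compatible with the data, and that an interval spanning 15% is inconclusive on the 15% hypothesis.
4. Report the mean and SD of the paired change, for planning later work. Medians and ranges can stay as descriptive summaries.

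No new data, visits or patients are needed. The cost is a few sentences, and the conclusions may have to be more cautious.
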